2.3 Tertiary/Exploratory/Correlative Objectives**Specific Aim 3:**

To determine if variations in gut microbiome and their metabolites between participants explains the variability associated with different doses of acute mirabegron administration.

We will correlate measures of body composition derived from dual-energy X-ray absorptiometry (DEXA) to primary and secondary outcome measures.

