3.3 Tertiary/Exploratory/Correlative Outcome Measures

Specific Aim 3:

Serum mirabegron metabolites will be used to determine the mirabegron metabolism using metabolomics.

Body composition will be measured using DEXA once after informed consent during the screening visit. We will run exploratory correlational analyses among the other physiological data collected and body composition.

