12.0 Statistical Considerations

Specific Aim 1

Power Analysis: Using data from Loh et al. (2) we expect to observe an effect size (δ) of 0.90 for the comparison of resting energy expenditure in the placebo condition versus 200 mg of mirabegron. Given this effect size, 10 participants will be needed to achieve a power of 0.99 with an alpha level set at 0.05. To account for possible attrition, we plan on recruiting up to 30 participants.

Statistical Approach: We will compare the primary (i.e., thermogenesis) and secondary (i.e., core temperature, skin temperature, heart rate, blood pressure, indices of shivering, thermal perceptions, and infrared thermography images) dependent variables using mixed effects ANOVA (i.e., mirabegron dose x time) followed by Tukey's post hoc procedure if a significant interaction or main effect is found from the ANOVA analyses. We will also calculate the thermogenesis area under the curve for each dose of mirabegron. These values will be compared using repeated measures ANOVA followed by Tukey's post hoc procedure if a significant main effect is found from the ANOVA analysis. We will also perform correlation analyses to determine the relation between body composition and our primary and secondary dependent variables. The alpha level will be set at $P < 0.05$ for all analyses.

Specific Aim 2

Power Analysis: Similar to Specific Aim 1 and the data from Loh et al. (2), we expect to observe an effect size (δ) of 0.90 for the comparison of rectal temperature in the placebo condition versus the mirabegron condition. Given this effect size, 10 participants will be needed to achieve a power of 0.99 with an alpha level set at 0.05. To account for possible attrition, we plan on recruiting up to 30 participants.

Statistical Approach: The primary (i.e., core temperature deflection point) and secondary (i.e., onset of shivering inflection point) dependent variables from the mirabegron and placebo trials will be compared using paired t-tests to determine if mirabegron improves cold-water immersion tolerance. Mixed effects ANOVA will be used to compare the remaining dependent variables between conditions (i.e., mirabegron vs. placebo) and across time. If a significant

interaction or main effect results from the ANOVA analyses, we will use the Holm-Sidak post hoc test to determine where differences exist. The alpha level will be set at $P < 0.05$ for all analyses.

Specific Aim 3

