Power Analysis: This aim is being conducted as an exploratory aim in conjunction with Specific Aim 1. As such, to be consistent, we expect to observe an effect size (δ) of 0.90 for the comparison of the gut microbiota in the placebo condition versus 200 mg of mirabegron. Given this effect size, 10 participants will be needed to achieve a power of 0.99 with an alpha level set at 0.05. To account for possible attrition, we plan on recruiting up to 30 participants.

Statistical Approach:

Principal Coordinate Analysis will be performed with group samples and any outliers will be identified. T-tests, and/or ANOVA will be performed to identify significant differences. Statistical analysis to detect variation between samples will be carried out using student t-test or Mann-Whitney test depending on data distribution. Multivariate statistics will be incorporated in a web-based tool Metastats, which can reveal, with high confidence, discriminatory functions between the replicated metagenome dataset of the gut microbiota of humans. In addition, the ShotgunFunctionalizeR and/or Primer E packages will be used for this analysis.

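### Specific Aim 3 asks whether microbiome and metabolite variation explains dose-related variability, but no specified analysis ties them to an outcome, and the 0.99 power belongs to a different question

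*Combined protocol and SAP*

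**What the plan says.** - **Objective (section 2.3).** "To determine if variations in gut microbiome and their metabolites between participants explains the variability associated with different doses of acute mirabegron administration". This is a question about association, with the participant as the unit.
- **Power (section 12.0, Specific Aim 3).** An effect size of 0.90, 10 participants and power 0.99 at alpha 0.05 are stated "for the comparison of the gut microbiota in the placebo condition versus 200 mg of mirabegron", with recruitment of up to 30.
- **Methods (same section).** The sentence on comparing samples reads "Statistical analysis to detect variation between samples will be carried out using student t-test or Mann-Whitney test depending on data distribution". Ahead of it the plan sets out an ordination step: "Principal Coordinate Analysis will be performed with group samples and any outliers will be identified". A further short sentence covers testing in general terms: "T-tests, and/or ANOVA will be performed to identify significant differences". Metastats is named for multivariate discrimination, and ShotgunFunctionalizeR and/or Primer E as software. No response variable appears with any of these.
- **Correlations.** Section 2.3: "We will correlate measures of body composition derived from dual-energy X-ray absorptiometry (DEXA) to primary and secondary outcome measures". Section 12.0, Specific Aim 1: "We will also perform correlation analyses to determine the relation between body composition and our primary and secondary dependent variables". Section 3.3, below the Aim 3 heading: "We will run exploratory correlational analyses among the other physiological data collected and body composition".
- **Samples (sections 3.1, 5.0 and 7.0).** Aim 3 uses the four-visit Aim 1 crossover. Blood is drawn before intake and after the 6-hour protocol. Stool comes from the first bowel movement after each visit.

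**The concern.** A shift in microbiota from placebo to 200 mg, present or absent, does not show whether people with different microbiomes respond to or handle the drug differently. The objective needs an analysis that relates a microbiome or metabolite measure to a named outcome. The plan gives neither the analysis nor the outcome, which could be thermogenic response, drug exposure or drug metabolism. Outcome, predictor and grouping would then be chosen after many taxa and metabolites have been seen, while the document carries a power of 0.99 that a reader may credit to the aim.

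The second part concerns repeated samples. Mann-Whitney assumes independent samples, and here every participant contributes to every condition. Neither the groups nor the samples to be compared are defined, so the effect of ignoring the repetition depends on which contrast is meant.

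**Working it through.** **1. The plan's own figure.** Inputs from section 12.0: effect size 0.90, n = 10, alpha 0.05 (taken as two-sided). Paired t-test: noncentrality 0.90 × √10 = 2.846 on 9 df gives power 0.717, and 25 participants are needed for 0.99. The stated 0.99 is approached only under unstated assumptions. One is 0.90 scaled by the raw SD with within-person correlation about 0.8 (0.978) to 0.82 (0.987). Another is 0.90 read as Cohen's f (0.997 or more with four conditions). Under every reading the powered quantity is a difference between conditions. The shortfall is a separate matter; the point here does not depend on it.

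**2. Is the objective's analysis given elsewhere?** Sections 3.1, 3.3, 5.0 and 7.0 cover what Aim 3 measures and how samples are handled. The three correlation statements name body composition and do not name microbiome or metabolites. No correlation, regression, covariate or interaction analysis links the latter to an outcome.

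**3. What n = 10 to 30 offers for the objective.** One feature against one outcome, Pearson correlation, two-sided, 80% power. Fisher z: |r| = tanh[(z(1−α/2) + 0.842)/√(n−3)].
- α = 0.05, n = 10: tanh(2.802/√7) = 0.785; n = 20: tanh(2.802/√17) = 0.591; n = 30: tanh(2.802/√27) = 0.492. Simulation gives 0.762, 0.580 and 0.485; the approximation is visibly off only at n = 10.
- α = 0.05/20 = 0.0025, the strictest false-discovery step for an assumed 20 features: tanh(3.865/√7) = 0.898, 0.734 and 0.631. Simulation gives 0.896, 0.732 and 0.630.
- Power at an assumed |r| = 0.5 for n = 10/20/30 (simulated): 0.33/0.64/0.83 for one test, and 0.05/0.21/0.43 at α = 0.0025.

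**4. Pairing, if conditions are compared.** Normal data, unit SD, two-sided 0.05. The documents give no within-person correlation ρ, so 0.3/0.5/0.7 is assumed. Paired power uses d/√(2(1−ρ)); unpaired power is simulated.

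| n, difference | t unpaired | t paired | Mann-Whitney | signed-rank |
|---|---|---|---|---|
| 10, 0.9 SD | 0.48/0.48/0.48 | 0.57/0.72/0.90 | 0.42/0.42/0.42 | 0.55/0.70/0.89 |
| 30, 0.9 SD | 0.96/0.98/0.99 | 0.98/1.00/1.00 | 0.94/0.96/0.99 | 0.97/1.00/1.00 |
| 30, 0.5 SD | 0.47/0.47/0.47 | 0.61/0.75/0.93 | 0.45/0.44/0.42 | 0.60/0.74/0.92 |

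The unpaired t-test's type I error at n = 10 is 0.023/0.010/0.002, below nominal. At ρ = 0 pairing gains nothing (n = 10, 0.9 SD: 0.48 unpaired, 0.44 paired).

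**5. Repeats, if groups of participants are compared.** With one value per person, Mann-Whitney is valid. With all four samples per person pooled as if independent (two equal groups, no true difference), its type I error is about 0.15/0.22/0.27 at ρ = 0.3/0.5/0.7, for n = 10 and n = 30 alike.

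**The case against.** The strongest defence is that Aim 3 is exploratory. Sections 2.3 and 12.0 say so, and this lowers the stakes. It does not supply the missing analysis, and the plan itself attaches a formal power claim to the aim.

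Several stronger readings are tempting, and the documents do not support them:
- *That only difference tests are planned.* Ordination, a discriminatory tool and Primer E are also listed. What is missing is an outcome for any of them.
- *That the plan rules out microbiome correlations.* The Aim 1 sentence on correlations names body composition but excludes nothing, and the section 3.3 sentence is loosely worded. The fair statement is that no such analysis is specified.
- *That every Aim 3 test is unpaired.* The t-test and ANOVA could be meant as paired or repeated-measures; section 12.0 does not say. Only Mann-Whitney is an independent-samples test by definition.
- *That ignoring the pairing creates false positives.* For contrasts between conditions, which the power sentence suggests, it does the opposite. Inflation arises only if repeat samples are pooled across groups of participants, and no such groups are defined.
- *That 0.90 and 0.63 are the detectable |r| under false-discovery control.* They apply at the strictest step. If several features are truly associated, smaller values suffice.

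**Conclusion.** The concern holds for Aim 3. Followed exactly, the plan tests whether the microbiota differ between samples or conditions. It does not test whether microbiome or metabolite variation explains variability between participants, and its 0.99 power refers only to placebo versus 200 mg. For the stated objective, 10 participants could detect only a very strong association, and 30 a fairly strong one (step 3 of the working).

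The test-choice fault is smaller and conditional. For condition contrasts it is conservative: a material loss at n = 10 or for a 0.5 SD difference, and a small one at n = 30 and 0.9 SD. It becomes anticonservative only under the pooled reading. These sizes rest on normal data, an assumed within-person correlation of 0.3 to 0.7 and, for multiplicity, an assumed 20 features. The mismatch between objective and analysis rests on none of them. The data already planned could support a suitable analysis.

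**What to change.** 1. **Tests.** Define the groups and the unit of analysis. For contrasts between conditions, use a paired t-test, a Wilcoxon signed-rank test, or a mixed model with participant as random effect and condition and visit as fixed effects. For multivariate composition, permute within participant. For contrasts between groups of participants, use one value per participant.
2. **Objective.** Add an analysis, labelled exploratory, with the participant as unit. The sponsor names the outcome: dose-minus-placebo thermogenesis area under the curve (stating which dose or doses), or serum or fecal mirabegron or metabolite level. Relate it to a few pre-named microbiome or metabolite summaries with false-discovery control. Stool follows each visit's placebo or drug intake, so report an association and not a baseline predictor. Averaging the summaries over visits is an optional safeguard against shared visit-day effects; it protects fully only if those effects are equal across visits.
3. **Power.** State that the 0.99 refers only to placebo versus 200 mg. Add the |r| detectable with 80% power: about 0.76 (n = 10, simulated; 0.79 by Fisher z) or 0.49 (n = 30) for one test, and about 0.90 or 0.63 at alpha 0.05/20, described as the strictest false-discovery step for an assumed 20 features.

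Cost: SAP wording, some analysis time and a less favourable stated figure. The samples and thermogenesis data are already planned at the Aim 1 visits.

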13.0 Statistical Data Management

Primary data will be collected via a data acquisition system (PowerLab) and stored electronically on a password protected computer. The storage location will be backed up manually every week. Quality assurance steps will be confirmed by plotting the data prior to formal analyses. Outliers will be identified and checked for authenticity in the database and other original data documents. Extraction and cleaning of data that will be used for analysis will be carried out after each study visit.

14.0 Privacy/Confidentiality Issues

Informed consent will be obtained, and the testing procedures will be completed in a closed, private laboratory setting at the School of Public Health (SPH), with only the participant and investigators present.

All testing will take place in a closed, private laboratory setting in the School of Public Health. All participants will be assigned an identification number, which will then be used when recording and analyzing data. A code list containing the participants names and identification numbers will be stored separately in a locked filing cabinet and will only be available to the investigators. The reports generated as a result of this investigation will not identify individual subjects. Data will be collected and stored on password protected computers located in the Human Performance Laboratories, which are always kept locked. Any paper data will be stored in a locked filing cabinet inside a locked office. Primary data are backed up by manual download to an encrypted flash drive once per week, which is then stored in a separate locked office in a locked filing cabinet accessible only to the investigators.

While testing is in progress, a sign will be outside the laboratory door to prevent people not associated with the study from entering.

15.0 Follow-up and Record Retention

We anticipate that all participants will be enrolled within 24 months. Any identifiable data (e.g., signed consent forms) will be maintained as required by law. De-identified data will be stored indefinitely. Only investigators will have full access to data. All electronic data will be kept on password protected computers, while paper data will remain in locked file cabinets.

17.0 Appendix

17.1 Payment schedule

Specific Aim 1: Participants will be compensated in the form of a gift card for \$495 for completing the informed consent/screening visit and the four study visits. Compensation will occur on or after the final visit to the laboratory. If participants do not complete the study, they will be compensated for their time spent in the laboratory at a rate of \$15/hour paid by gift card.

Specific Aim 2: Participants will be compensated in the form of a gift card for \$165 for completing the informed consent/screening visit and both study visits. Compensation will occur on or after the final visit to the laboratory. If participants do not complete the study, they will be compensated for their time spent in the laboratory at a rate of \$15/hour paid by gift card.

Specific Aim 3: Participants will be compensated in the form of a gift card for \$100 for completing the informed consent/screening visit and bringing their samples to the laboratory. Compensation will occur on or after the final visit to the laboratory. If participants do not complete the study, they will be compensated at a rate of \$25/sample paid by gift card.

17.2 Attachments

The following Questionnaires have been included as attachments:

- International Physical Activity Questionnaire (IPAQ)
- Physical Activity Readiness Questionnaire Plus (PAR-Q+)
- Healthy History and Demographics Questionnaire
- Health History Update Questionnaire

The following Recruitment tools have also been included as attachments:

- Recruitment flyer
- Email script
- Verbal script
- Phone script
